6.7 Risk Benefit Assessment

Treatment options for patients with *RAS* WT, PI3K mutated mCRC after progression with standard chemo- and targeted therapy including anti-EGFR containing regimens remain poor. The PI3K/protein kinase B (AKT)/mTOR signalling pathway, which controls numerous cellular functions, is frequently deregulated in these tumours.

Hyperactivation of the PI3K cascade is one of the principal mechanisms of resistance involved in the lack of response to anti-EGFR antibodies.

Because PI3K is the most proximal component of the pathway, targeting PI3K itself rather than AKT or mTOR might induce a pronounced inhibition of the downstream components and reverse eventual resistance to previous treatments. A number of PI3K inhibitors are under clinical investigation in different type of tumours, including pan-PI3K inhibitors targeting all four isoforms of class I PI3K (e.g. buparlisib, pictilisib), as well as isoform-selective inhibitors, especially PI3K α inhibitors, such as taselisib and alpelisib. Considering the high frequency of toxicity of pan-PI3K inhibitors, some of them have been discontinued despite the evidence of clinical activity, mostly in combination (i.e. buparlisib).

MEN1611 is a potent, selective class I PI3K inhibitor with a strong inhibitory activity against PI3K α which has shown cytotoxic activity in *in vitro* and *in vivo* models as single agent and in combination. Moreover, in the FIH study conducted by Chugai Pharmaceutical, MEN1611 has shown a good safety profile, in line with the class of agent, furthermore an encouraging anti-tumour activity, resulting in disease stabilization in 24% of treated patients, has been observed (PA-001 EU Clinical Study Report). Therefore, given the lack of standard therapeutic options for the selected patient population, the pharmacological properties and acceptable toxicological profile shown in preclinical and clinical studies, the risk-benefit assessment is considered favourable in the context of the clinical study.

Considering the above, the intent is exploring the safety and activity of MEN1611 plus cetuximab in patients with *PIK3CA* mutated, *RAS* WT mCRC progressed over at least two previous lines of irinotecan, oxaliplatin, 5-FU and anti-EGFR antibodies-containing regimens. If this study demonstrates an efficacy signal, MEN1611 could offer a new therapeutic approach in the treatment of this setting.

In this study, MEN1611 treatment will be continued until objective disease progression is documented or another criterion for discontinuation (e.g. unacceptable toxicity, withdrawal of consent) is met, for patients affected by mCRC. To mitigate the risk of the administration of the study treatment and to guarantee the patients' safety during the study participation, the following measures have been applied in accordance with European Medicines Agency (EMA) guidelines ([37](#)):

- 1) It was decided to consider a starting dose of 48 mg BID according to the data included in the Investigator's Brochure (IB), it being the MTD in the FIH study. The 48 mg given BID offered a good safety profile, as MEN1611 was well tolerated and successfully inhibited the PI3K pathway.
- 2) Although MEN1611 did not show to induce any mood disorder in the clinical studies up to date, patients having any serious and/or unstable pre-existing psychiatric or neurologic illness or other conditions that could interfere with patient's safety are to be excluded, considering the toxicity profile of the class of drug (i.e. buparlisib).
- 3) MEN1611 as other PI3K inhibitors are reported to cause hyperglycaemia; for this reason, patients with uncontrolled diabetes mellitus (glycated haemoglobin [HbA1c] > 7%) and fasting plasma glucose (FPG) > 126 mg/dL will not be included in the study; a strict monitoring of safety laboratory tests including blood sugar levels as well as recording of any AEs will be done at each visit and appropriate therapy will be started immediately at occurrence.
- 4) Pre-clinical study showed effects on the lymphoid/hematopoietic system, such as decreases in reticulocytes, lymphocytes and bone marrow cells; for this reason, a strict monitoring of safety laboratory test including haematology as well as recording of any AEs will be done at each visit and appropriate supportive care will be started immediately. In the B-PRECISE-01 (as of 30 January 2023) at the 48 mg BID dose (n=58), 20 (35.71%) patients had TEAEs in the SOC Blood and Lymphatic System Disorders (regardless of causality): 19 (33.9%) anaemia, 18 (32.14%) leukopenia, 5 (8.93%) neutropenia, 5 (8.93%) thrombocytopenia, and 2 (3.57%) lymphopenia. Out of them, 6 (10.71%) were of CTCAE (v4.03) \geq grade 3 severity, 4 (7.14%) anaemia, with neutropenia and thrombocytopenia occurring to one patient (1.79 %) each.
- 5) Diarrhoea is a class toxicity of PI3K inhibitors (38). In the FIH Chugai Pharmaceutical study (PA-001EU), one of the most common side effects was gastrointestinal disorders. In the B-PRECISE-01 (as of 30 January 2023) at the 48 mg BID dose, 37 (66.1%) patients had diarrhoea (regardless of causality), it was of CTCAE (v4.03) \geq grade 3 severity in 6 (10.7%) patients. Furthermore, diarrhoea is associated with the use of cetuximab and it is a frequent symptom associated with tumour. We have clearly stated in the exclusion criteria that National

Cancer Institute Common Terminology Criteria for Adverse Events version 5.0 (NCI CTCAE v5.0) Grade ≥ 2 diarrhoea, which is not resolved in the week prior to the start of treatment, will be considered an exclusion criterion. Physical examination and laboratory tests will be performed at each visit and appropriate supportive care will be started immediately at occurrence as per investigator judgement.

- 6) Considering the toxicity profile of the class of PI3K inhibitors, preliminary data from B-PRECISE-01 study (as of 30 January 2023) at the 48 mg BID dose, shows 32 (57.14%) patients had TEAEs in the SOC Skin and Subcutaneous Tissue Disorders (regardless of causality), it was of CTCAE (v4.03) \geq grade 3 severity in 2 (3.6%) patients. Based on that, the combination of MEN1611 with cetuximab, cutaneous reaction is considered a potential risk for the patients.

[figure not shown]
The most frequent cutaneous toxic effects reported in clinical studies with PI3K inhibitors have been maculopapular eruption, pruritus, and dry skin. In the B-PRECISE-01 study the most common TEAEs were rash in 15 (26.8%) and pruritus in 6 (10.71%) patients. For this reason a complete clinical examination including skin will be performed at screening and throughout the study at each study visit.

In addition, due to the known cetuximab skin toxicity, patients will receive general educational and prophylactic measures (see Section 8.4.6). Consultation with a dermatologist shall be performed in case skin toxicity Grade ≥ 3 is assessed (the AE has to be followed until resolution to Grade 1). The frequency of dermatological visits can be increased upon Investigator's judgement.

- 7) As highlighted above, no AE due to drug phototoxicity was reported in the FIH study. In the B-PRECISE-01 study (as of 30 January 2023) at the 48 mg BID dose, 10 (17.9%) patients had TEAEs in the SOC Eye Disorders, all of them were CTCAE v4.03 grade 1 or 2 severity, the most common were: dry eye in 4 (7.1%), blepharitis in 3 (5.4%) and vision blurred in 2 (3.6%). Considering the eye toxicity associated with cetuximab, we want to exclude any potential risk for the patients under treatment with the combination. Patients will receive complete physical examination at each cycle including eyes. Ophthalmic visits shall be performed for any Grade ≥ 2 eye disorder and repeated bi-weekly until resolution to Grade 1 (the frequency can be increased upon Investigator's judgement).

- 8) Respiratory disorders including fatal cases have been reported in patients treated within the EGFR-pathway (both cetuximab and PI3K inhibitors) (38). Confounding or contributing factors, such as concomitant chemotherapy known to be associated with interstitial lung disease (ILD), and pre-existing pulmonary diseases were frequent in fatal cases. Patients with known active or uncontrolled pulmonary dysfunction are excluded from this study. Patients enrolled will be regularly questioned about pulmonary symptoms during the study. Should pulmonary symptoms appear during or after cetuximab treatment, a detailed description is required and investigators should use their discretion in ordering such diagnostic procedures as are necessary to elicit an accurate diagnosis. If pneumonitis/ILD is diagnosed, cetuximab and MEN1611 must be discontinued and the patient be treated appropriately.
- 9) MEN1611 affected the blood pressure (BP), with transient hypertension (approx. 20 mmHg compared to the pre-dose values) in telemetered cynomolgus monkeys from 2 to 6 hours after dosing at 0.5, 1.5, 3.7 and 9 mg/kg, but with no effects on other parameters of the cardiovascular system. In the B-PRECISE-01 study, (as of 30 January 2023) at the 48 mg BID dose, 5 (8.9%) patients had hypertension (regardless of causality), most of them were CTCAE v4.03 grade 1 or 2 severity, and 1 of them of grade 3. A strict monitoring of safety includes vital sign and BP measurement. Therefore, to prevent such potential risks, patients with uncontrolled hypertension (defined as persistent BP of $\geq 150/90$ mmHg despite treatment, measured on at least 2 separate occasions) will be not included in the study.
- 10) As far as treatment with cetuximab is concerned, in order to mitigate the potential risk of severe and infusion reactions, for the first administration, patients will be monitored during cetuximab infusion and for at least 1 hour after end of the infusion. In order to mitigate the potential risk of severe and fast progressing infusion reactions, premedication including a corticosteroid and a histamine-1 (H1) receptor antagonist (e.g. d-chlorpheniramine or diphenhydramine) is recommended. Availability of resuscitation equipment must be ensured. In addition, patients will be informed about the possibility of such a late onset and instructed to contact the physician if symptoms or signs of an infusion-related reaction occur (see Section 8.4.5).
- 11) The potential for DDI between MEN1611 and cetuximab is relatively low; indeed, considering the pathways involved in the elimination of a small molecule (e.g. renal and

biliary excretion, CYP450-mediated metabolism) and a monoclonal antibody (e.g. renal metabolism, immunogenicity, Fc receptors, target mediated clearance), most of the possible DDI mechanisms can be ruled out in the case of MEN1611 and cetuximab. Nevertheless, MEN1611 PK will be characterized in combination with cetuximab and compared with MEN1611 PK as single agent, to assess any potential interaction.

6.7.1 Risk Benefit Assessment for COVID-19 Pandemic

There is currently an outbreak of respiratory disease (COVID-19) caused by a novel coronavirus SARS-CoV-2 that was first detected in Wuhan City, Hubei Province, China in 2019. This new virus has rapidly spread across the globe causing the World Health Organization (WHO) to declare a pandemic situation on March 12, 2020. In response to the pandemic, the health authorities have issued recommendations on the further conduct of clinical studies. Accordingly, risk assessments of involvement in the trial with added challenges due to COVID-19 and mitigation measures need to be taken into consideration in all clinical studies to protect patients, site staff and the society as a whole.

This is a phase Ib/II clinical trial for heavily pre-treated patients with metastatic colorectal cancer with few tolerable and efficacious therapeutic available options as per standard of care. The eligibility of patients to the study will be evaluated by the treating physician/PI/sub-investigator after individual assessment that the clinical benefit of the investigational products will outweigh the risk of contracting the SARS-CoV-2 infection without compromising the safety of the patients and care providers.

Measures to mitigate the additional risks caused by COVID-19 are:

- Current national laws and local recommendations for prevention of pandemic will be strictly adhered.
- Patients will be encouraged to follow strictly local mitigation recommendations when ambulatory (e.g. social distancing, use of mask, etc.).
- Access to Clinical site will be as per local COVID-19 control measures.
- Based on the local circumstances, to be reassessed on an ongoing basis, additional measures will be considered for implementation including:
 - Interruption or slowing down of recruitment of new trial participants;
 - Postponement of activation of sites that have not yet been initiated;
 - Transfer of trial participants to investigational sites away from risk zones, or closer to their home;
 - re-distribution among sites, in case of shortage of study drug;
 - Increase of IMP kits dispensation during the site visits to cover longer periods of time and/or distribution of IMP to study participant's home;
 - Cetuximab administration to be performed at local outpatient facilities closer to participants' home, in case the trial participants cannot reach the site;
 - Safety laboratory tests to be performed at local laboratory or participant's home, in case the trial participants cannot reach the site;
 - Remote consent could be collected (when applicable as per site policy).

7 STUDY OBJECTIVES

7.1 Primary Objectives

Step 1:

- To determine the RP2D of MEN1611 when administered orally in combination with cetuximab to patients with *PIK3CA* mCRC failing irinotecan, oxaliplatin, 5-FU, and anti-EGFR containing regimens.

[figure not shown]
Step 2:

- To assess the anti-tumour activity of MEN1611 in combination with cetuximab in patients with *PIK3CA* mutated mCRC failing irinotecan, oxaliplatin, 5-FU, and anti-EGFR containing regimens.

7.2 Secondary Objectives

- To assess the safety and tolerability of MEN1611 in combination with cetuximab.
- To assess the PK profile of MEN1611 when given in combination with cetuximab.

7.3 Exploratory Objectives

8 INVESTIGATIONAL PLAN

8.1 Overall Study Design and Plan Description

This is an open-label, dose-confirmation and cohort expansion, multicentre, Phase Ib/II study to be conducted in approximately 29 sites in Europe and US.

The study will consist of 2 sequential steps:

Step 1 (Confirmation of Dose for Cohort Expansion):

[REDACTED]

Step 2 (Cohort Expansion Phase):

[REDACTED]

8.2 Selection of Study Population

Patients meeting all the following criteria will be eligible for entry into the pre-screening:

1. Able to give written informed consent.
2. mCRC.
3. Progression or recurrence following prior anti-EGFR containing regimen and at least in second line of treatment for mCRC.
4. Known *N-K-RAS* (exons 2, 3 and 4) WT status.
5. Known *BRAF* WT or unknown *BRAF* status.
6. Male and female aged ≥ 18 years.

Patients will **not be eligible for entry into the pre-screening** if they meet ANY of the following exclusion criteria:

1. Patients with a known *PIK3CA* WT status
Note: this exclusion criterion does not apply if *PIK3CA* WT status was assessed before the last anti-EGFR containing regimen.
2. Previous treatment with PI3K inhibitor.
3. Hypersensitivity and/or contraindication to MEN1611, cetuximab or to any component of the formulations.
4. Inability or unwillingness to abide by the study protocol; legal incapacity or limited legal capacity.

At the Pre-screening Visit, all patients will sign the ICF to perform mutational analysis for *PIK3CA*, *BRAF* and *N-K-RAS* in plasma (ctDNA centrally analysed). Inclusion into the study will be done based on the results of the ctDNA.

Eligibility of patients to the study will be checked at Screening Visit and re-checked prior to the start of any treatment.

Patients will be included only if they meet all of the patient inclusion criteria (Section 8.2.1) and none of the exclusion criteria (Section 8.2.2), providing written informed consent.

8.2.1 Inclusion Criteria

Patients meeting all the following criteria at Screening Visit will be eligible for entry into the study:

1. Able to give written informed consent before any study related procedure.

2. Histological documentation of adenocarcinoma of the colon or rectum with radiological evidence of progressive disease after last treatment received.
3. Progression or recurrence following irinotecan, oxaliplatin, fluoropyrimidine containing regimen and anti-EGFR containing regimens for metastatic disease. Patients who have a history of intolerance of irinotecan-based therapy or who are ineligible to receive irinotecan are also eligible as long as they have received a prior oxaliplatin-based therapy. Patients who have a history of intolerance of oxaliplatin-based therapy or who are ineligible to receive oxaliplatin are also eligible as long as they have received a prior irinotecan-based therapy.
4. Best response according to Response Evaluation Criteria in Solid Tumours (RECIST) criteria to the last anti-EGFR containing regimen of PR or SD for at least 4 months.
5. Measurable disease according to RECIST criteria, version 1.1.
6. Having a tumour *N-K-RAS* (exons 2, 3 and 4) and *BRAF* WT harbouring a *PIK3CA* mutation, as per centrally-analysed ctDNA during the [pre]-screening period using a validated test.
7. Eastern Cooperative Oncology Group (ECOG) performance status (PS) of 0 or 1.
8. Life expectancy \geq 12 weeks.
9. Adequate cardiac function as defined by left ventricular ejection fraction of \geq 50% measured by a multigated acquisition (MUGA) scan or echocardiography (ECHO).
10. Adequate bone marrow function as defined by absolute neutrophil count (ANC) of $\geq 1.5 \times 10^9/L$, platelet count of $\geq 100.0 \times 10^9/L$ and haemoglobin of $\geq 9 \text{ g/dL}$.
11. Adequate liver function, as determined by total bilirubin within upper limit of normal (ULN) ($\leq 1.5 \times \text{ULN}$ if documented liver involvement; $\leq 3 \times \text{ULN}$ with direct bilirubin $\leq 1.5 \times \text{ULN}$ in case of patients with coexisting known Gilbert's disease) and/or AST and alanine aminotransferase (ALT) $\leq 2.5 \times \text{ULN}$ ($\leq 5 \times \text{ULN}$ if liver metastases).
12. Adequate renal function assessed by creatinine clearance $\geq 50 \text{ mL/min}$ (calculated by Cockcroft-Gault formula).
13. Adequate electrolytes (serum potassium and magnesium levels within institutional normal limits). Replacement treatment to achieve adequate electrolytes levels is allowed.
14. Not pregnant, not breastfeeding, and at least 1 of the following conditions applies:
 - a) Not a woman of childbearing potential (WOCBP) (see Appendix I, Section 13.1).

OR

 - b) A WOCBP who agrees to use highly effective contraception 4 weeks before the first dose of the study treatment, during the treatment period and for 6 months following the last dose of the study treatment. Patients should not breastfeed during and at least for 6 months after the last dose of the study treatment.

15. Male patient who is surgically sterile or male patient who is willing to agree and have his female partners (if WOCBP) agreeing with the true abstinence (refrain from heterosexual intercourse) or who agrees to use and to have his female partners (if WOCBP) using barrier contraceptive measures during the entire study treatment period and for 6 months after the last administration of study treatment, and agrees to refrain from donating sperm during the entire study treatment period and for 6 months after the last administration of study treatment.

Note: Inclusion criteria 7 and 10 to 13 (if applicable) will be re-evaluated prior to the start of any study treatment (Day 1 of Cycle 1).

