	
5. Measurable disease according to RECIST criteria, version 1.1.6. Having a tumour N-K-RAS (exons 2, 3 and 4) and BRAF wild-type harbouring a PIK3CA mutation, as per centrally-analysed ctDNA during the [pre]-screening period using a validated test.7. Eastern Cooperative Oncology Group (ECOG) performance status (PS) of 0 or 1.8. Life expectancy \geq 12 weeks.9. Adequate cardiac function as defined by left ventricular ejection fraction of $\geq 50\%$ measured by a multigated acquisition (MUGA) scan or echocardiography (ECHO).10. Adequate bone marrow function as defined by ANC of $\geq 1.5 \times 10^9/L$, platelet count of $\geq 100.0 \times 10^9/L$ and haemoglobin of $\geq 9 \text{ g/dL}$.11. Adequate liver function, as determined by total bilirubin within ULN ($\leq 1.5 \times \text{ULN}$ if documented liver involvement; $\leq 3 \times \text{ULN}$ with direct bilirubin $\leq 1.5 \times \text{ULN}$ in case of patients with coexisting known Gilbert's disease) and/or AST and ALT $\leq 2.5 \times \text{ULN}$ ($\leq 5 \times \text{ULN}$ if liver metastases).12. Adequate renal function assessed by creatinine clearance $\geq 50 \text{ mL/min}$ (calculated by Cockcroft-Gault formula).13. Adequate electrolytes (serum potassium and magnesium levels within institutional normal limits). Replacement treatment to achieve adequate electrolytes levels is allowed.14. Not pregnant, not breastfeeding, and at least 1 of the following conditions applies:
a) Not a woman of childbearing potential (WOCBP) (see Appendix I, Section 13.1). ORb) A WOCBP who agrees to use highly effective contraception 4 weeks before the first dose of the study treatment, during the treatment period and for 6 months following the last dose of the study treatment. Patients
--	---

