5.7 Protocol/Protocol Modifications

The protocol must be read thoroughly by everyone, the information therein, concerns and the instructions must be exactly followed.

Changes in the study protocol will require a protocol amendment. Such amendments will be agreed upon and approved in writing by all signatories of the protocol. If amendments are substantial, i.e. they are likely to have an impact on the safety of the patients, or to change the interpretation of the scientific documents on which the trial is based or the scientific validity of the study results, significantly alter the nature of the management or conduct of the study, or impair the quality or safety of the investigational drugs, or if they are otherwise significant, the IRB/IECs and the CAs in the participating countries have to approve these amendments before implementation.

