6.6.3 Clinical Experience

In the PA-001 EU dose-escalation first-in-human (FIH) study, conducted by Chugai Pharmaceutical, MEN1611 was administered to patients with advanced solid tumours for which there was no standard treatment available. The study was conducted in 4 clinical centres from August 2010 until December 2012.

Of the 39 patients enrolled in PA-001 EU study, 38 patients were included in the safety population. MEN1611 was generally well tolerated and the majority of adverse events (AEs) and drug-related AEs were Grade 1 or 2 and reversible. The most common drug-related AEs ($\geq 20\%$ in total) were diarrhoea (34%), nausea (32%), fatigue (29%), stomatitis (26%) and decreased appetite (21%). The commonly reported Grade ≥ 3 AEs ($\geq 10\%$ in total) were anaemia (21%), diarrhoea (16%) and hyperglycaemia (13%). These events were restored when MEN1611 dose was decreased and/or discontinued.

Dose-limiting toxicities (DLTs) were reported in 1/7 patients in the 48 mg twice daily (BID) cohort (aspartate aminotransferase [AST] increased), 2/3 patients in the 72 mg BID cohort (fatigue and encephalopathy) and 2/5 patients in the 56 mg BID cohort (diarrhoea and mucosal inflammation). MEN1611 was well tolerated up to total daily doses of 96 mg when administrated once daily (QD) or BID. The MTD of MEN1611 was determined to be 48 mg BID. No deaths due to AEs were reported in this study. AEs leading to discontinuation of study treatment and AEs leading to modification of study treatment were reported in 8/38 and 13/38 patients, respectively.

At single and repeated doses, MEN1611 was absorbed and eliminated rapidly, with a low contribution of renal excretion on its total elimination. MEN1611 exposure AUC and C_{max} was subject to large

variability. In QD cohorts there was no clear evidence of accumulation, whereas a potential for MEN1611 accumulation was observed in the BID regimen. After QD administration, saturation of exposure was observed in 56 to 96 mg dose range at single dose and 32 to 96 mg dose range at repeat dose, suggesting that MEN1611 exhibits non-linear PK at these doses.

[figure not shown]

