10.4 Quality Control/Quality Assurance

10.4.1 Study Monitoring

This study will be monitored in accordance with the ICH Guidelines for GCP. Monitoring will be carried out under the responsibility of the CRO (IQVIATM). The site monitor will perform visits to the study sites during the study conduct. Facilities, study treatment, storage area, storage conditions for biological samples, eCRF, patient's source data and all other study documentation will be inspected/reviewed by the site monitor for adherence to the protocol and GCP. At each site visit, the monitor will review the eCRFs for completion and accuracy. Accuracy will be checked by performing source data verification that is a direct comparison of the entries made onto the eCRFs against the appropriate source documentation. Any resulting discrepancies will be reviewed with the Investigator and his/her staff. The Investigator agrees to allow access to all study-related materials needed for the proper review of study conduct and to assist the monitor during the monitoring visits and during the data cleaning process. Monitoring procedures require that 100% of data are source data verified starting from the date of the Screening informed consent signature to the End of Study, particularly focusing on informed consents, adherence to inclusion/exclusion criteria, drug accountability, documentation of SAEs and the proper recording of efficacy and safety measurements. All monitoring activities will be described in detail in the study-specific monitoring plan.

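### Inclusion criterion 11 joins the bilirubin and AST/ALT limits with 'and/or', so read literally either set alone is enough for adequate liver function at Screening and on Day 1

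*Protocol*

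**What the plan says.** Criterion 11 in Protocol section 8.2.1 has two parts.

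- **Bilirubin:** total bilirubin no higher than ULN. The ceiling rises to 1.5 x ULN with documented liver involvement, and to 3 x ULN in known Gilbert's disease provided direct bilirubin is at most 1.5 x ULN.
- **Transaminases:** AST and ALT at most 2.5 x ULN, or 5 x ULN with liver metastases.

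The parts are joined by "and/or AST and alanine aminotransferase (ALT". The synopsis has "and/or AST and ALT" at the same point, so the connector appears twice.

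The note closing section 8.2.1 carries the criterion forward to the first dosing day: "Inclusion criteria 7 and 10 to 13 (if applicable) will be re-evaluated prior to the start of any study treatment". Section 8.2 adds the rule across criteria: "Patients will be included only if they meet all of the patient inclusion criteria". That rule makes criterion 11 mandatory, but it does not say whether both parts of criterion 11 are needed.

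**The concern.** In ordinary logic *and/or* is an inclusive *or*. On that reading the criterion is satisfied by one set of limits, and the other set has no ceiling at all. The Day 1 re-check applies the same text and so cannot close the gap.

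Two things are at stake. The first is patient safety at entry. The second is consistent eligibility: the study runs at "approximately 29 sites in Europe and US", and with this wording one site can require both sets of limits while another accepts either, each with a defensible reading of the text.

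The protocol gives some reason to care about the liver. Section 6.6.3 reports that in the first-in-human study dose-limiting toxicities "were reported in 1/7 patients in the 48 mg twice daily (BID) cohort (aspartate aminotransferase [AST] increased"), and 48 mg BID is the starting dose here.

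**Working it through.** The plan gives no figure to reproduce. The check is a comparison of texts and a truth table, followed by a look at how strong the clinical signal is.

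**1. Logic of criterion 11.** Let B = bilirubin limits met and T = AST and ALT limits met.

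| B | T | As written (B and/or T) | With *and* |
|---|---|---|---|
| yes | yes | pass | pass |
| yes | no | pass | fail |
| no | yes | pass | fail |
| no | no | fail | fail |

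Three of four combinations pass as written and one passes under *and*. These are types of patient, not proportions of patients.

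**2. Two hypothetical patients without liver involvement.**

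- Bilirubin within ULN, ALT 8 x ULN: criterion 11 is met through B, although ALT is 8 / 2.5 = 3.2 times its limit.
- AST and ALT 2 x ULN, bilirubin 4 x ULN: criterion 11 is met through T, although bilirubin is 4 / 1 = 4 times its limit.

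Both fail under *and*.

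**3. What the sponsor probably meant.** Criterion 10, immediately above, joins its neutrophil, platelet and haemoglobin limits with a plain *and*. The allowances inside criterion 11 point the same way. Under the literal reading, a patient with Gilbert's disease and acceptable transaminases passes whatever the bilirubin, so the 3 x ULN ceiling and the direct-bilirubin condition do nothing. The 5 x ULN allowance for liver metastases likewise does nothing when bilirubin is acceptable. Allowances graded this carefully make sense only if each part binds.

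**4. Search for another hepatic entry limit.**

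- No other readable inclusion or exclusion criterion gives a bilirubin, AST or ALT threshold.
- Exclusions 10 and 16 (section 8.2.2) can keep out an unsafe patient, but they rest on judgement.
- Section 8.5.4.6 has the Investigator assess out-of-range values clinically, without an entry threshold.
- Chemistry is repeated on Days 8, 15 and 22 of Cycle 1 (section 8.5.1), after dosing has begun.
- Exclusion 17 is redacted, and the content of section 8.4.4 (MEN1611 toxicity management) is not shown. A hepatic limit at entry or on treatment could stand in either.

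**5. Strength of the clinical signal.** Input: 1 AST event in 7 patients at 48 mg BID (section 6.6.3).

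- Estimate: 1/7 = 14.3%.
- Exact 95% lower limit: 1 - 0.975^(1/7) = 0.0036, or 0.4%.
- Exact 95% upper limit: p solving (1 - p)^7 + 7p(1 - p)^6 = 0.025, which gives p = 0.579, or 57.9%.
- Patients with a reported dose-limiting toxicity in that study: 1 + 2 + 2 = 5, of whom 1 had a hepatic event. Those at 56 and 72 mg BID were not hepatic.

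**6. Exposure.** Section 6.6.3 says renal excretion contributes little to MEN1611 elimination. Item 11 of section 6.7 names biliary excretion and CYP450 metabolism as example routes for a small molecule. From these one can infer that poor liver function might raise exposure. The protocol gives no hepatic-impairment data, and the example routes are not a description of MEN1611 itself.

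**The case against.** The strongest reply is that this is a drafting slip which no competent investigator would exploit. The criterion concerns adequate liver function, and an ALT of 8 x ULN is hard to call adequate. Such a patient must also have ECOG 0 or 1 and a life expectancy of at least 12 weeks, avoid exclusions 10 and 16, and have eligibility reconfirmed on Day 1, when chemistry is drawn again. Nothing shows that any site has used the loose reading. The safety case is thin too: one event in 7, with nothing reported on that patient's baseline liver function. Section 6.6.3 describes MEN1611 as well tolerated in a further 56 patients at 48 mg BID in the breast cancer study, and none of the 11 risk measures in section 6.7 is hepatic.

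Most of this stands, and it limits the point to a minor one. It does not remove it, because the safeguards are judgements while criterion 11 exists to supply a number.

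A reader might also infer more than the documents support:

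- **That the protocol demands the literal reading.** Section 5.7 says "the instructions must be exactly followed", but this is general compliance text. It gives no rule for resolving an ambiguous connector.
- **That monitoring would miss a patient who met only one set of limits.** Section 10.4.1 names "adherence to inclusion/exclusion criteria" as a focus and leaves the detail to a separate monitoring plan. Deviation categories are still to be defined (Protocol 9.4; SAP 7.4.2). How such a patient would be handled is unknown.
- **That the response rate would shift.** The efficacy population is restricted to eligible patients (Protocol 9.2; SAP 7.3), but the readable text does not define the term. Accrual runs to 40 evaluable patients, so a patient found ineligible during accrual might simply not count towards the 40. No effect on the response rate can be calculated.
- **That the Step 1 dose decision is affected.** The dose-limiting toxicity definition is not readable, the safety committee has discretion over the tolerable dose (section 8.5.5.1), and Step 1 may already be complete.

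**Conclusion.** The point holds as a wording fault in an operative safety criterion. As written, criterion 11 is met by either the bilirubin limits or the AST/ALT limits, at Screening and on Day 1, and nothing readable supplies the missing requirement. The intent was probably *and*.

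Its importance is low. The number of patients affected cannot be derived, and no sample size, power or error rate depends on it. The clinical relevance rests on a single AST event with a very wide interval. The suggestion of higher exposure is an inference and should be presented as one. The conclusion assumes that neither redacted exclusion 17 nor the unseen section 8.4.4 contains a limit that would close the gap. Even if one did, criterion 11 would still read ambiguously and should be corrected.

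**What to change.** Replace *and/or* with *and* in criterion 11 of section 8.2.1 and of the synopsis, so that both sets of limits must be met. Keep the allowances for liver involvement, Gilbert's disease and liver metastases. The Day 1 note then needs no change. Send sites a written clarification until the next amendment. If enrolment has already closed, list at the data review meeting (Protocol 9.4) any patient who met only one set of limits.

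The cost is small. It is one word in two places, and no new test is needed, because the chemistry panel in Table 8-8 already includes total and direct bilirubin, ALT and AST. Entry becomes slightly stricter for patients who would have passed on one part only. If the change is judged substantial under section 5.7, ethics committees and authorities must approve it first. The safety gain reaches only patients not yet enrolled, and the readable text does not say how many remain.
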